- Prior medical history: Patients' available history in the iKnowMed (iKM) EHR will vary based on the length of disease and the time within The US Oncology Network. Disease characteristics such as time of NSCLC diagnosis and date of metastatic

disease will take into account patients' available medical history. The prior medical history period will end the day prior to the index date-1.

• Follow-up: Patients will be followed through the end of the study observation period, date of last visit or date of death, whichever occurs first. For analysis, patients will have a potential of at least 6 months of follow-up duration; however, patients will have variable follow-up time periods, depending on their index dates and last contact dates.

9.3.1. Phase 1 and 2 (original study) and Phase 3 (refresh study) population Inclusion criteria

Patients must meet all of the following inclusion criteria to be eligible for inclusion in the study:

- 1. Patients with a documented diagnosis of NSCLC.
- 2. Patients \geq 18 years of age at initial recorded diagnosis of NSCLC.
- 3. Patients who received treatment with alectinib within The US Oncology Network or Non-Network sites during the study identification period.
- 4. During the study observation period, patients observed with at least 2 visits⁴ after the index date-1.

Exclusion criteria

Patients meeting any of the following criteria will not be included in the study:

- 1. Receipt of treatment indicated for another primary cancer or diagnosis of another primary cancer (with the exception of non-melanotic skin cancer), within 5 years of index date-1 will be excluded.
- 2. Patients enrolled in clinical trials prior to receiving alectinib during the study ID period (index date-1), will be excluded.

⁴ Visits are defined as physical encounters with the practice, detected by vital sign records. The second and third visits must be observed after the index date-1 to demonstrate continuity of care. There is no required time span between the additional visits and the index date-1.

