Reason for ALK inhibitor (alectinib, and subsequent treatment) treatment discontinuation	Chart review	Treatment characteristics	Study observation period	Data for alectinib and subsequent treatment discontinuation reason will exclusively come from chart review. Reviewers will be asked to select reason(s) as explicitly documented in patients' charts. If available, reason patients discontinued treatment will be abstracted: Completion of therapy Provider-documented disease progression Death Insurance/cost-related Loss to follow-up Patient preference Toxicity Other No information Reviewers will specify other reasons; these will be reported if any represent >5% of patients.	
ALK inhibitor treatment sequencing	iKM structured data + chart review	Treatment pattern	Study observation period	ALK inhibitor treatment paths (e.g. initiate crizotinib followed by ceritinib, initiate crizotinib followed by alectinib, etc.)	
Front-line alectinib	iKM structured data + chart review	Treatment pattern	Study observation period	First treatment administration of alectinib not preceded by any other product for NSCLC therapy except up to 3 months of chemotherapy and immunotherapy preceding alectinib therapy initiation to classify patient as receiving 1L alectinib	
Clinical outcomes					
Last US Oncology Network visit date	iKM structured data + chart review	Clinical outcomes	Study observation period	Each patient's most recent visit date, prior to or on close of study observation period, in the structured data will be recorded. A visit is defined as a physician encounter with the practice where either treatment is given, or vital signs are recorded. For patients with a death date, this last visit date should occur prior to the death date.	

Table 1. Study variables and operational definitions

Variable	Source(s)	Role(s) in study	Period of measurement	Operational definition
				This will not be reported separately; it will be used in calculating the patient's available follow-up time as a descriptive measure. Available follow-up time = Integer (latest of last visit date or death date – index date +1).7

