Death date	iKM structured data + limited access death master file (LADMF) + chart review	Clinical outcomes	Study observation period	Date of death will be captured from the LADMF as well as iKM. If dates conflict between the 2 sources, the LADMF date will be prioritized. If severe data discordance is observed (i.e., death is reported to occur prior to the index date), then the iKM death date will be used.
Vital status	iKM structured data + LADMF + chart review (derived)	Clinical outcomes	Study observation period	Patients without a date of death in either the LADMF or iKM will be assumed to be alive at the end of the study. Those with a date of death in either LADMF or iKM will be flagged as deceased.
ALK inhibitor (alectinib and stratified by subsequent treatment) duration of therapy (DOT)	iKM structured data + chart review (derived)	Treatment characteristics	Study observation period	An intent to treat approach will be used. DOT will be defined as duration of time (in months) between alectinib initiation and discontinuation, or the last administration date of alectinib, or start date of a subsequent ALK inhibitor, or evidence of new non-ALK inhibitor treatment (as a proxy for evidence of discontinuation) will be used as a stop date. There may be some patients who do not have evidence of discontinuation or who do not move on to a subsequent therapy.
				Descriptive statistics (mean, median) and K-M methodology will be calculated from initiation of alectinib, until evidence of discontinuation for any reason, including but not limited to a treatment stop date, a last alectinib administration date, evidence of new ALK inhibitor treatment or non-ALK inhibitor treatment, death or check-in in a hospice. Patients who do not have evidence of discontinuing, starting new therapy, or whose last prescription date is <30 days from the end of

Table 1. Study variables and operational definitions

Variable	Source(s)	Role(s) in	Period of	Operational definition
		study	measurement	
				the study period, will be censored at last visit date or end of study period.

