Overall survival (OS) (alectinib and stratified by subsequent treatment)	iKM structured data + LADMF + chart review (derived)	Clinical outcomes	Study observation period	OS will be defined as the interval (in months) between alectinib start date and the date of death (any cause) as documented in the LADMF and the iKM EHR database. OS will be reported for overall alectinib and stratified by subsequent treatment. Patients who did not die within the study observation period will be censored on the study end date or the last visit date available in the dataset, whichever occurred first. OS will be analyzed using the Kaplan-Meier method with 95% CIs, and summary tables of the number of events and censored patients 3, 6, 12, 18, and 24 months.
Progression date after index date (physician- assessed)	Chart review	Clinical outcomes	Study observation period	Physician-assessed disease progression (and corresponding date of note) recorded from physician's progress notes in Chart Review.
Progression- free survival (alectinib, and subsequent treatment)	iKM structured data + LADMF + chart review (derived)	Clinical outcomes	Study observation period	The PFS will be measured from the initiation of alectinib to the date of progression or date of death due to any cause, censoring patients who are still alive at the end of the study observation period and did not progress at the last visit date. PFS will be reported for overall alectinib and stratified by subsequent treatment. The PFS will be estimated in weeks using the Kaplan-Meier method with 95% CIs, and summary tables of the number of events and censored patients at 3, 6, 12, 18, and 24 months.

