The Limited Access Death Master File (LADMF) of the Social Security Administration will be an additional source of vital status (death), in addition to death dates recorded in the EHR. Common patient identifiers (patient identification, name, and birth date) will be used to link patients from the iKM data warehouse and iKM chart review. The social security number (SSN) will be used to link patients from iKM and LADMF data sources. All patients within iKM are assigned a unique patient identifier by iKM version (e.g., some large practices have separate installations by location). When linking to the LADMF, patient SSN is used. Some practices do not collect SSN and some patients may not report it. In all cases, reported deaths captured in iKM will supplement the Social Security Administration data.

Data from all sources and any derived variables will be merged into one master dataset for analysis. Data will be handled in compliance with the Health Insurance Portability and Accountability Act (HIPAA) and Health Information Technology for Economic and Clinical Health (HITECH).

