All descriptive tables will be presented for each of the study cohorts defined above and, as supported by the final sample size, stratified by front-line alectinib and non front-line alectinib treatment groups.

For Phase 3 exploratory objectives, descriptive analyses will be conducted to evaluate the demographic, clinical and treatment characteristics among patients treated with lorlatinib. Results will be reported in aggregate. Categorical variables (e.g., ECOG performance status) will be reported as frequency and percentage. Continuous variables such as age will be reported as mean, standard deviation, median and range (minimum-maximum). In the case of missing observations, the number and percentage of missing values will be reported.

Clinical outcomes

ALK inhibitor DOT, OS, PFS will be assessed using the Kaplan-Meier method with 95% CIs, and summary tables of the number of events and censored patients at 3, 6, 12, 18, and 24 months. Further details about these calculations are presented below and in Table 1.

Clinical outcome results will be presented by study cohort and stratified by front-line alectinib and non-front line alectinib (pending sample size).

Overall survival (OS) will be defined as the interval between start date of alectinib to the date of death as documented in the LADMF and/or iKM EHR database. Patients who did not die will be censored on the study end date or the last visit date available in the database, whichever occurred first. In order to handle censoring, the Kaplan-Meier method will be used to calculate median overall survival with 95% confidence intervals (in number of months). Additionally, 3, 6, 12, 18, and 24-month survival probabilities will be reported. OS will be estimated for the full study population and stratified by study cohort. Log-rank tests will be used to assess statistical differences.

Duration of Therapy (DOT) for ALK inhibitors: An intent to treat approach will be used. DOT will be defined as duration of time (in months) between alectinib treatment initiation and discontinuation, or the last administration date of alectinib, or start date of a subsequent ALK inhibitor, initiation of any subsequent non-ALK inhibitor treatment (as a proxy for evidence of discontinuation), death or check-in in a hospice will be used as a stop date.

There may be some patients who do not have evidence of discontinuation or who do not move on to a subsequent therapy.

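### The OS rule counts deaths after the last visit but no survival time after it; the net bias has unknown sign, and nothing planned would reveal it

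*Combined protocol and SAP*

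**What the plan says.** **Event.** Section 9.8.3 defines OS as "the interval between start date of alectinib to the date of death as documented in the LADMF and/or iKM EHR database". No limit is set on how long after the last visit a death may fall.

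**Censoring.** The same section states: "Patients who did not die will be censored on the study end date or the last visit date available in the database", and the earlier of these two dates applies. The OS row of Table 1 (Section 9.4) gives the same rule: "Patients who did not die within the study observation period will be censored on the study end date or the last visit date", again at the earlier of the two.

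**Vital status.** Table 1 adds: "Patients without a date of death in either the LADMF or iKM will be assumed to be alive at the end of the study".

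**Follow-up.** The follow-up bullet in Section 9.3 ends observation at the end of the period, "date of last visit or date of death, whichever occurs first". Sections 4, 9.1 and 9.2 use the last patient record in place of the last visit. The last-visit row of Table 1 takes the later date: "Available follow-up time = Integer (latest of last visit date or death date". That row also expects the last visit to come before death.

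**Linkage.** LADMF is matched on SSN, and Section 9.5 warns: "Some practices do not collect SSN and some patients may not report it". Section 9.10.1 says that care outside the network is not captured.

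Section 9.8 says that no separate SAP will be written. No linkage share, count of deaths after the last visit, or alternative censoring analysis is planned.

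**The concern.** Kaplan-Meier needs censoring that does not depend on the outcome. Here, a patient who stops attending and later dies can be found in LADMF and stays in the risk set up to the death. A patient who stops attending on the same day and lives is removed on that day. Late events are kept while the matching late survival time is discarded, which pulls the curve down. Deaths that neither source records pull it up, because those patients appear as censored.

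OS is Objectives 4 and 10. Section 9.8.3 plans medians, survival at 3, 6, 12, 18 and 24 months, and log-rank tests between cohorts. If cohorts differ in how often patients leave or in how many have a usable SSN, the rule could create or hide a difference between them.

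**Working it through.** The protocol gives no OS assumption, loss rate or capture rate, so there is no planned figure to reproduce. The rule was applied to simulated patients instead.

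**From the documents.** Phase 3 identification runs from 01 June 2017 to 31 August 2020, which is 39 months. Observation ends on 31 August 2021, at 51 months. The plan's rule is: time = date of death if a death is captured by study end, otherwise the earlier of last visit and study end.

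**Assumed, because the documents do not say.** Exponential survival with median 40 months; uniform entry; non-informative departure from the practice at 10% or 20% per year; last visit up to 1 month before death, departure or cutoff; several death-capture rates. There were 400,000 patients per scenario. Repeat runs differ by about 0.2 percentage points and 0.2 months.

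**True value.** S(24) = 0.5^(24/40) = 0.660.

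**The plan's rule:**

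| Leave per year | In-practice deaths captured | Later deaths captured | 24-month OS (true 66.0%) | Median (true 40) |
|---|---|---|---|---|
| 10% | 100% | 70% | 64.1% | 35.9 |
| 20% | 100% | 70% | 62.3% | 33.0 |
| 10% | 90% | 70% | 66.8% | 38.8 |
| 10% | 80% | 80% | 69.3% | 41.6 |
| 10% | 70% | 70% | not quoted | 46.0 |

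In the first two rows, 24-month OS is low by 66.0 − 64.1 = 1.9 and 66.0 − 62.3 = 3.7 points, and the median by 40 − 35.9 = 4.1 and 40 − 33.0 = 7.0 months. In the third row the two measures err in opposite directions. In the fourth row both are high, by 69.3 − 66.0 = 3.3 points and 41.6 − 40 = 1.6 months.

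**Isolating the asymmetry.** With true median 48 months, visits up to 3 months apart and every death captured, true S(24) = 0.5^(24/48) = 0.707. The plan's rule reads 0.702, 0.676 and 0.649 at 0%, 10% and 20% leaving per year, with medians of 44.9, 38.9 and 34.4. Two symmetric rules recover medians of 47.5 to 48.0: carrying survivors to study end, or cutting deaths and survivors alike one visit gap after the last visit.

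**Where symmetry is not enough.** In the same setting with 80% of deaths captured and 10% leaving, 24-month OS reads 0.731 under the plan's rule, 0.766 with survivors carried to study end and 0.760 with the common window, against 0.707. Symmetry removes the downward part only.

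**The wording side by side.** Table 1 expects the last visit to precede death. Read literally, the Section 9.3 rule then stops follow-up before a death that the OS definition counts. The last-record wording in Sections 4, 9.1 and 9.2 is looser, since a death entry could be a patient record. The follow-up row of Table 1 agrees with the OS definition in letting a death extend follow-up.

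**The case against.** The strongest objection concerns direction. A reader might infer that OS is simply biased low. That needs nearly complete death capture, and Section 9.5 says linkage is incomplete. The sign reverses within ranges that the documents do not rule out, so this objection stands.

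A reader might also infer that the plan states two censoring rules giving two curves. It does not. Section 9.8.3 and the OS row of Table 1 agree. The vital-status sentence is a flag with no censoring date, and the follow-up row is a descriptive measure. Nor would an analyst take the general wording of Section 9.3 as cancelling the specific OS definition. These are passages to reconcile.

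The size at planned landmarks is also modest. In the 10% loss scenario with 70% of later deaths captured, the 12-month fall is about 0.5 points. With a median of 81.6 months (the cited 6.8 years, which runs from diagnosis rather than alectinib start), 24-month OS falls from 81.6% to 80.2%.

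Finally, study-end censoring is no cure. With 90% of all deaths captured and 10% leaving, it gives a median of 46.9 against a true 40, while the plan's rule gives 37.9. An alternative must therefore be offered as a check and not as a corrected estimate.

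The objection does not remove the outcome-dependent censoring in the stated rule, or the lack of any output that would show its effect. The study being descriptive does not help, because the survival estimates are themselves the result.

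**Conclusion.** The point holds as a matter of asymmetry and non-reporting. The rule lowers OS for captured deaths, missed deaths raise it, and the documents do not give the rates needed to tell which prevails. Under the assumed rates with median 40 months, 24-month OS could read about 2 to 4 points low or about 3 points high, and the median 4 to 7 months low or 1.6 to 6 months high. These figures illustrate scale; they do not estimate the bias in this study. They depend on the assumed exponential survival, departure rates, visit spacing and capture, and on departure being unrelated to prognosis. The wording conflict in Section 9.3 is real but minor. The issue should be settled before the Phase 3 analysis.

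**What to change.** 1. Keep the stated OS analysis, and define last contact once for all sections.
2. Report the share of patients with an SSN usable for LADMF linkage, and the number and timing of deaths after last contact, overall and by cohort.
3. Pre-specify two OS sensitivity analyses: (a) SSN-linked patients only, with those lacking a death record censored at study end, or at the LADMF cutoff if earlier; (b) all patients, with deaths and survivors both cut at the same fixed window after last contact. Set the window length in advance.
4. Present both as checks, with no direction assumed. A gap from the main curve in (b) reflects the asymmetry, while (a) also reflects the change of population. Neither shows how many deaths were missed.
5. Align the follow-up wording in Sections 4, 9.1, 9.2 and 9.3 and in the last-visit and vital-status rows of Table 1 with the OS definition.

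The cost is two further Kaplan-Meier runs, a small table and text edits. The linked subset will be smaller and may not be representative, since SSN collection varies by practice, and registry capture within it may still be incomplete.

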9.8.3. Statistical methods

Description of study enrollment

To be included in the study patients must meet each of the inclusion criteria and none of the exclusion criteria listed in Section 9.3.1. Counts of patients excluded for each criterion will be summarized.

Additionally, the counts of patients to be classified into the following subgroups will be presented⁵:

- Cohort A: All alectinib treated patients (overall population)
- Cohort B (Alectinib only cohort): Alectinib treatment ongoing, or discontinued and no subsequent treatment⁶
- Cohort C: Alectinib followed by treatment X (top 3 most frequent)
- Cohort D: Alectinib followed by treatment Y (top 3 most frequent)
- Cohort E: Alectinib followed by treatment Z (top 3 most frequent)

Description of patient demographic, clinical and treatment characteristics

Descriptive analyses will be conducted to evaluate the demographic, clinical and treatment characteristics overall, as well as for each of the study cohorts. Results will be reported in

⁵ Final cohorts will be decided upon sample size. Patients receiving chemotherapy after initiating alectinib will be included in the patient sample

⁶ Patients with ongoing alectibin treatment, patients who discontinued alectinib and patients who did not have a subsequent treatment may be analyzed as separate cohorts depending on sample size of patients

aggregate. Categorical variables (e.g., ECOG performance status) will be reported as frequency and percentage. Continuous variables such as age will be reported as mean, standard deviation, median and range (minimum-maximum). In the case of missing observations, the number and percentage of missing values will be reported.

For comparative analysis, i.e. comparing 2 or more treatment groups (e.g., ALK inhibitor sequences) or strata (front-line alectinib and non front-line alectinib), statistical significance will be reported with level of statistical significance based on p = 0.05 level as well as 95% confidence intervals.

Chi-square testing will be used to assess associations between categorical variables when patient counts for single cells within the results tables are greater or equal to 5. When distribution cannot be assumed to be Chi-square, then Fisher's exact test will be used. Depending on normality, Analysis of variance (ANOVA)/t-tests or Kruskall-Wallis tests will be used for continuous variables. An alpha level of 0.05 will be the primary criterion for statistical significance of this study.

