Descriptive statistics (mean, median) and K-M methodology will be calculated from initiation of alectinib, until evidence of discontinuation for any reason, including but not limited to a treatment stop date, a last alectinib administration date, or evidence of new ALK inhibitor treatment or non-ALK inhibitor treatment. Patients who do not have evidence of discontinuing, starting new therapy, or whose last prescription date is <30 days from the end of the study period, will be censored at last visit date or end of study period.

$$DOT = (\frac{\textit{date of ALK treatment discontinuation - index date} + 1}{30.4375})$$

Progression-free survival: The PFS will be measured from the initiation of alectinib to the date of progression or date of death due to any cause, censoring patients who are still alive at the end of the study observation period and did not progress at the last visit date. Progression will be clinician-noted progression as noted per physician notes only, not by traditional Response Evaluation Criteria in Solid Tumors (RECIST) imaging, as this is impacted by frequency of imaging and may not be assessed the same across groups in daily clinical practice. Patients who did not progress or die will be censored on the study end date or the last visit date available in the database, whichever occurred first. The PFS will be estimated in months using the Kaplan-Meier method with 95% CIs, and summary tables of the number of events and censored patients at 3, 6, 12, 18, and 24 months. PFS will be estimated for the full study population and separately by study cohort. Log-rank tests will be used to explore statistical differences.

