The iKM system is used for clinical practice reasons, not solely for research purposes. As such, associations but not causality can be detected, thus bias may be introduced by confounding factors. For example, data may be collected with an intent-to-treat approach, meaning based on when treatment is assigned rather than received. In particular, it will not be possible to determine if oral therapies were dispensed or taken; therefore, we'll use an intent-to-treat approach for analysis, with the assumption that all prescribed oral therapies were taken. Likewise, patients who do and do not receive the treatment at one point in time may be fundamentally different than those who received treatment during the observation period. These confounding factors are most likely to affect the outcomes being considered for this estimation study.

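### OS and PFS are compared between groups only by an unadjusted log-rank test, which gives no between-group estimate or interval and leaves the collected prognostic factors unused

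*Combined protocol and SAP*

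**What the plan says.** Section 9.8.3 (Clinical outcomes) plans Kaplan-Meier estimation of OS and PFS with 95% CIs. For OS this includes the median, and "Additionally, 3, 6, 12, 18, and 24-month survival probabilities will be reported". On grouping: "OS will be estimated for the full study population and stratified by study cohort". Outcomes are also to be shown by front-line and non-front-line alectinib if numbers allow.

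The between-group method for OS is "Log-rank tests will be used to assess statistical differences", and for PFS "Log-rank tests will be used to explore statistical differences". No regression model, hazard ratio, covariate-stratified test, weighting or matching is planned anywhere. Hazard ratios appear only in the background account of a cited trial.

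Earlier in the same section, for comparisons of treatment groups or of front-line and non-front-line strata, the protocol says "statistical significance will be reported with level of statistical significance based on p = 0.05 level as well as 95% confidence intervals". It then makes alpha 0.05 the main criterion of significance for the study. Section 9.8 says no separate analysis plan will be written.

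Table 1 collects age, ECOG status and metastatic sites including brain and CNS as baseline characteristics (age is also an eligibility item). Section 9.10.1 concedes confounding: "These confounding factors are most likely to affect the outcomes being considered for this estimation study".

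**The concern.** A log-rank test returns a p-value. It does not say how large a difference is or how precisely it is known, and in this form it treats the groups as if they had the same prognosis. These groups are formed by clinical choice and by line of therapy, so they may well differ in age, performance status and CNS disease. With a significance threshold attached, a difference in case mix can be reported as a difference in survival, with no adjusted figure against which to check it. In the smaller cohorts the opposite error is likely: a non-significant p-value may be read as similarity when the data are compatible with a halving or a doubling of the hazard.

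**Working it through.** The protocol gives no event count, effect size or power calculation for these comparisons, so there is no figure of its own to reproduce. The numbers below show scale only.

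**1. What is planned and what is absent**

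| Item | Per group | Between groups |
|---|---|---|
| OS | Kaplan-Meier median with CI; probabilities at 3 to 24 months | log-rank p-value only |
| PFS | Kaplan-Meier with CI; event and censoring counts | log-rank p-value only |
| Age, ECOG, brain/CNS metastasis | described at baseline | not used for OS or PFS |

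**2. Precision in cohorts C to E**

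Inputs: 521 patients (section 9.6, Phase 3 feasibility) and 20 to 30% with a later therapy (section 9.6, from the Phase 1/2 set of 293). Assumptions: an even split over three cohorts and 40 to 60% deaths.

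- Patients with a later therapy: 0.20 × 521 = 104; 0.30 × 521 = 156. Per cohort: about 35 to 52.
- Deaths in a two-cohort comparison: 2 × 35 × 0.4 = 28, up to 2 × 52 × 0.6 = 62.
- 95% CI around a hazard ratio of 1, using SE(log HR) = √(4/deaths): at 28 deaths, SE = 0.378 and the CI is 0.48 to 2.10; at 62 deaths, SE = 0.253 and the CI is 0.61 to 1.64.

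A p-value alone shows none of this width.

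**3. False rejection from case mix, simple formula**

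Assumptions, none from the documents: two equal groups, no true difference, ECOG 2+ in 15% v 30% or 10% v 30%, ECOG hazard ratio 2.5 to 3, two-sided 0.05.

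Apparent HR = [1 + p1(HR − 1)] / [1 + p0(HR − 1)]

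- 15% v 30%: 1.45/1.225 = 1.18 (HR 2.5); 1.60/1.30 = 1.23 (HR 3).
- 10% v 30%: 1.45/1.15 = 1.26; 1.60/1.20 = 1.33.

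Rejection probability = Φ(z − 1.96) + Φ(−z − 1.96), with z = ln(apparent HR) × √deaths / 2.

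- 28 deaths, apparent HR 1.18: z = 0.45, probability 0.07.
- 62 deaths, apparent HR 1.23: z = 0.82, probability 0.13.

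So for two of cohorts C to E, with 15% v 30%, the figure is about 7 to 13%. At 120 deaths the formula gives 15 to 21% (15% v 30%) and 25 to 35% (10% v 30%). It uses the hazard ratio at time zero, however, and ignores that high-risk patients die earlier and leave the risk set. It therefore overstates the effect at larger event counts.

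**4. The same scenarios by simulation**

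Added assumptions: exponential survival with a 36-month median at the reference level, censoring uniform between 12 and 51 months, about 128 deaths.

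| ECOG 2+ | Unadjusted log-rank rejects | Stratified on ECOG |
|---|---|---|
| 15% v 30% | about 13 to 17% | about 5% |
| 10% v 30% | about 20 to 25% | about 5% |

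Repeat runs moved the lower ends by a point or two, to 12% and 18%. An event count of this order suits front-line v non-front-line, not two of cohorts C to E.

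**The case against.** The strongest reply is that the study is descriptive. Section 9.6 says so and declines a power calculation. The outcome objectives are to estimate or examine, and the PFS test is only exploratory. Section 9.10.1 limits the study to association. This lowers the weight of the point but does not remove it: a purely descriptive study needs no alpha, and this one sets 0.05 and tests OS and PFS.

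Several stronger readings are tempting, and the documents do not support them:

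- *That section 9.10.1 predicts confounding by age, ECOG or CNS disease.* It names none of these. Its examples are prescribed oral drugs assumed to have been taken, and patients treated at different times. The concession is general.
- *That the protocol promises a confidence interval for the survival contrast and fails to give it.* The sentence on 95% CIs sits under the description of patient characteristics, next to chi-square and ANOVA. Clinical outcomes have their own heading and their own Kaplan-Meier intervals.
- *That readers get no survival magnitude at all.* Medians, landmark probabilities, intervals and counts are planned by cohort, and baseline tables will make imbalance visible.
- *That front-line stratification already handles confounding.* It depends on sample size, covers one factor, and is itself a comparison to be tested. It cannot help PFS, because progression comes only from chart review and that sample is front-line.
- *That covariate adjustment would rescue the cohort comparisons.* Cohorts C to E are defined by treatment after alectinib, while OS and PFS start at alectinib initiation. Adjustment leaves that immortal time in place and could make the result look sounder than it is.

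**Conclusion.** The point holds in limited form. The plan's only between-group analysis of OS and PFS is an unadjusted test with a significance threshold. The missing parts are a between-group estimate with its interval and any use of prognostic factors already collected. Under the stated assumptions, false rejection is about 13 to 17% or 20 to 25% at about 128 deaths, and about 7 to 13% (15% v 30%) at the 28 to 62 deaths plausible for two of cohorts C to E. The ECOG prevalences, the hazard ratios and the death counts are all assumed, so these figures show a plausible size and are not a forecast. The change is worth making because it is cheap, but per-cohort reporting is unaffected and the descriptive aims stand without it.

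**What to change.** **Front-line v non-front-line, OS from alectinib start.** Replace the stand-alone log-rank test with a Cox hazard ratio and 95% CI, unadjusted and adjusted for a fixed list: age at index (derivable from date of birth), ECOG (0-1, 2+, unknown) and any brain/CNS metastasis. State in advance how the metastatic-site category for no information is handled. Leave out time since metastatic diagnosis, which largely overlaps with front-line status.

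**Cohorts B to E, OS and PFS.** Show Kaplan-Meier estimates with CIs and no significance test. Allow a model only if the comparison starts at index date-2, the covariates are re-derived at that date, and there are about 10 or more events per model parameter. One group term, age, two ECOG terms and one metastasis term make 5 parameters, or about 50 events, so many comparisons among C to E would stay untested.

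**Text.** Say that residual unmeasured confounding remains after adjustment.

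**Cost.** One protocol paragraph and one model pair. No new data are needed for the comparison from alectinib start. Table 1 defines metastatic sites only at index date-1, so a model from index date-2 may need re-extraction. The other costs are an unknown level for ECOG and no p-values for small cohorts.
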